# Funded by: NIH: Eunice Kennedy Shriver National Institute of Child Health and Human Development

Version Number: v.2.3

15 May 2023

Summary of Changes from Previous Version:

Affected Section(s)	Summary of Revisions Made	Rationale
1.2, 2.3.2, 4.1, 4.2, 4.3, 6.1.1, 6.1.2, 6.2, 9.2, 9.4.5	Low-Volume exercise group removed from protocol.	Reduce enrollment following COVID pandemic.
1.3	Clarification to criteria defining protocol deviation - updating number of days that create a deviation.	Reducing documentation burden associated with schedule deviations
2.3.1, 2.3.3, 5.2	Removal or MRI contraindication as exclusion criteria.	Low enrollment number. MRI data is not used for primary outcome. Removing this criterion may increase the number of eligible participants.

## STATEMENT OF COMPLIANCE

The protocol, informed consent form(s), recruitment materials, and all participant materials will be submitted to the Institutional Review Board (IRB) for review and approval. Approval of both the protocol and the consent form will be obtained before any participant is enrolled. Any amendment to the protocol will require review and approval by the IRB before the changes are implemented to the study. In addition, all changes to the consent form will be IRB-approved; a determination will be made regarding whether a new consent needs to be obtained from participants who provided consent, using a previously approved consent form.

Investigators and clinical trial site staff responsible for study conduct, management, or oversight will complete Human Subjects Protection training in best practices for research.

1	PROTOCOL SUMI	MARY
1.1	SYNOPSIS	
Titl	e: dy Description:	How do the neck muscles influence head acceleration during sport- associated impact events in high school athletes? Sport-related concussion is a common injury associated with significant short- and long-term disability in high school athletes. This project will study up to 72 healthy male and female soccer athletes to determine how neck strengthening exercise affects head acceleration during sport- associated impacts (AIM 1) and define the mechanism relating neck strength and neck muscle volume to head acceleration under different impact conditions (AIM 2). The long term goal of this project is to optimize neck strengthening exercise programs to decrease the risk of concussion in high school athletes.
Objectives:		Primary Objective (AIM 1): To determine the effect of manual resistance neck strengthening exercise on net head acceleration during simulated sport-associated impacts to the head (direct loading condition). Secondary Objective (AIM 1): To determine the effect of manual resistance neck strengthening exercise on net head acceleration during simulated sport-associated impacts to the body (indirect loading condition). Exploratory Objective (AIM 1): To determine the effect of manual resistance neck strengthening exercise over time on neck strength, cervical muscle volume, neuromuscular recruitment, and net head acceleration under direct and indirect loading as well as during voluntary soccer heading. Exploratory Objective (AIM 2): To determine the relative influences of baseline neck strength and cervical muscle volume on net head acceleration during simulated sport-associated impacts to the head and body with and without volitional, anticipatory cervical muscle pre- contraction to brace for the impact.

Endpoints:	Primary Endpoint: Mean area under the net head acceleration vs. time curve during direct loading, with anticipatory bracing, at Assessment Time Point 4.
	Secondary Endpoint: Mean area under the net head acceleration vs. time curve during indirect loading, with anticipatory bracing, at Assessment Time Point 4.
Study Population:	Up to 72 male and female high school soccer athletes in and around Ann Arbor Michigan.
Phase:	N/A
Description of	University of Michigan.
Sites/Facilities Enrolling	
Participants:	
Description of Study	Neck strengthening resistance exercise.
Intervention:	
Study Duration:	Approximately 60 months.
Participant Duration:	Approximately 4 months.

## 1.2 SCHEMA

Refer to Section 1.3, Schedule of Activities, for additional detail.

## 1.3 SCHEDULE OF ACTIVITIES (SOA)

	1	1									
	Initial Phone Screening Day -90 to -2	In-person screening/Intake Day -30 to -1	Baseline Assessment (#1) Day 1	Baseline MRI Day 1+/- 10 days	Exercise (2x/week) Weeks 1-4	Interim Assessment (#2) 28 +/- 10 days from #1	Exercise (2x/week) Weeks 5-8	Interim Assessment (#3) 28 +/- 10 days from #2	Exercise (2x/week) Weeks 9-12	Final Assessment (#4) 28 +/- 10 days from #3	Final MRI 28 +/- 10 days from #3
Procedures											
Eligibility review	Х	Х									
Demographics	Х	Х									
Medical and sport history	Х	Х									
Screening physical examination		Х									
Informed consent		Х									
Anthropometric assessment			Х			Х		Х		Х	
Randomized group allocation			Х								
Neck strength			Х			Х		Х		Х	
Cervical Muscle ultrasound			Х			Х		Х		Х	
Neck MRI				Х							Х
Cervical muscle activation			Х			Х		Х		Х	
Net head acceleration			Х			Х		Х		Х	
Exercise (2x/week) with strength					v		v		v		
coach					X		~		×		
Adverse event monitoring			Х	Х	Х	Х	Х	Х	Х	Х	Х

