*Kinematic measurements:* Light emitting diodes used with a high speed kinematic camera system may become hot to the touch when left to record continuously. Subjects could experience a minor superficial skin burn if a light emitting diode became too hot and was left in place, although this would be unlikely as the diodes are not affixed directly to the skin, but rather to a plastic plate surface affixed to the skin. The risk associated with this is considered non-serious. Likelihood: rare (< 1%).

*Skin preparation/application of skin adhesives:* Subjects may experience minor skin cuts or irritation associated with skin shaving or the adhesive backing on the surface EMG electrodes or other superficially adherent sensors. The risk associated with this is considered non-serious. Likelihood: infrequent (1-10%).

*Fitting of boil-and-bite mouth guards*: Subjects could receive minor burn to their hands or mouths while using boiling water to fit mouth guards to their mouth if direct contact with the boiling water occurred. The risk of burn is considered non-serious. Likelihood: rare (< 1%).

*Supervised exercise sessions:* Subjects are anticipated to experience delayed-onset muscle soreness following resistance training, which is a normal training-related phenomenon. The risk associated with this is considered non-serious. Likelihood: frequent (>25%). It is not expected that any serious training-related injuries will result from participation in study exercise sessions.

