## 4.3 JUSTIFICATION FOR DOSE

All subjects will exercise 2 days per week under the direct supervision of a study-assigned strength coach (National Strength and Conditioning Association Certified Strength and Conditioning Specialist, CSCS, certification), with a minimum of 1 day of rest between exercise sessions. Subjects will be assigned either to a high intensity neck strengthening exercise group or to a control exercise group performing only "shoulders-down" resistance exercises not directly targeting the neck. All exercises will be performed in accordance with National Strength and Conditioning Association standards. The neck strengthening program will include manual resistance exercises in sagittal-plane flexion and extension, coronal-plane lateral flexion to the left and right, and axial-plane rotation to the left and right, as well as dumbbell shoulder shrugs as previously described by our group. For each group, the exercise program

will progress in volume and intensity over the duration of the study, to accommodate muscular fitness adaptation. Such progression is considered vital to the long-term efficacy of resistance exercise programming.

The volume load of neck strengthening exercise will be calculated using a modified protocol previously employed by our group for the elbow flexors. For shoulder shrugs the volume load for each exercise session will be defined as the product of the dumbbell weight x the force of gravity (g= 9.8 m/s2) x the number of repetitions performed during the exercise session, to yield a volume load for the exercise session in N. During manual resistance exercise, the strength coach will hold a hand-held dynamometer against the subject's head to measure and record the force applied during manual resistance. For both dumbbell shrugs and manual resistance exercises, the total cumulative exercise volume load will be defined as the sum of the individual session volume loads over all exercise sessions completed by the subject. Since subjects assigned to the control group will not perform neck strengthening exercise, their exercise volume load will remain zero throughout the study.

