## 6.3 STUDY INTERVENTION COMPLIANCE

Subjects will be given the opportunity to make-up any missed exercise sessions within 7 days of the originally scheduled date, so long as at least one day of rest is scheduled between successive exercise sessions. Subjects will be considered to have successfully completed the exercise protocol if at least 20 of the 24 exercise sessions are attended, with no more than 2 missed sessions during any 4-week block.

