#### **Cervical muscle volume**

The total cervical muscle volume will be measured using magnetic resonance imaging (MRI) without contrast in a similar manner as previously described by [name]. The volume of individual cervical muscles will be calculated by integrating the cross sectional areas (CSA's) across slices multiplied by slice center-to-center spacing and total cervical muscle volume will be calculated as the sum of volumes of the individual muscles.

Estimated cervical muscle volume will also be calculated at each assessment using a predictive regression equation developed by [name] lab, which has been shown to accurately account for 87% of the variance in MRI-based total cervical muscle volume based on overall neck circumference and sex. We will further refine this regression-based estimate by incorporating the sonographic anatomical cross-sectional areas (CSA's) of key cervical muscles measured at each assessment time point, with validation of the expanded model using our MRI-based cervical muscle volume measurements. We will assess the sternocleidomastoid (SCM), upper trapezius (TRAP), splenius capitis (SPL), and semispinalis capitis (SEMI) muscles, which we have previously studied with acceptable test-retest reliability (intra-class correlation coefficients, ICC= .91 to ICC= .99) and validity as compared to criterion-standard MRI CSA measurements (R= .76 to R= .97). In the unlikely event that we are unable to adequately predict total cervical muscle volumes using [name] regression equation, we would alternatively assess cervical muscle hypertrophy using total neck circumference and the sonographic anatomical CSA measurements of the SCM, TRAP, SPL, and SEMI muscles.

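### The baseline MRI window runs to about Day 11, so a scan counted as baseline may follow the first exercise sessions; this affects exploratory muscle-volume results only

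*Combined protocol and SAP*

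**What the plan says.** Section 1.3 gives the scan its own column, "Baseline MRI Day 1+/- 10 days", so the latest permitted date is about Day 11. Randomized allocation, neck circumference, ultrasound and strength all belong to the Day 1 assessment. The next column is "Exercise (2x/week) Weeks 1-4", followed by "Interim Assessment (#2) 28 +/- 10 days from #1".

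Section 4.3 states "All subjects will exercise 2 days per week", "with a minimum of 1 day of rest between exercise sessions". Section 6.3 defines completion as "at least 20 of the 24 exercise sessions are attended". Under Section 6.1.1 both arms do general resistance work that includes shoulders and back. Only the neck arm adds manual neck resistance and shrugs, and Section 4.3 sets the control arm's neck volume load at zero.

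Section 9.4.4 compares the groups at baseline, cervical muscle attributes included, and describes this as their state before any assigned exercise. Section 8.1 (Cervical muscle volume) estimates volume at each assessment from circumference and sex, refined with ultrasound, "with validation of the expanded model using our MRI-based cervical muscle volume measurements". Section 9.4.5 lets the strength of that prediction decide whether MRI acquisition is cut back.

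**The concern.** A baseline value should precede the treatment whose effect is measured from it. Here the later half of the window falls after randomization and can fall after training has begun, and the neck-specific part of that training differs by arm. Two things are at stake.

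- **MRI volume change.** If the neck arm has already gained some volume by the time of a late scan, that gain is counted in the baseline and not in the change, so the between-arm difference comes out too small.
- **Equation validation.** A late scan sets a post-training MRI volume against circumference and ultrasound taken on Day 1. Disagreement caused by timing would then be read as prediction error, in a comparison that also governs how much MRI is done for the rest of the study.

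**Working it through.** **The plan's own figures.** Two sessions a week for 12 weeks is 2 × 12 = 24, as in Section 6.3. The plan gives no figure for exercise before the baseline scan.

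**When training starts.** No calendar day is given for session 1. Assessment #2 is nominally 28 days after #1, so a four-week block fits only if it starts soon after Day 1. The start day is left as an assumption and varied below.

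**Most sessions possible before a Day 11 scan**, with two per seven-day training week and at least one rest day between them:

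| First session | Possible session days | Most sessions | Share of 24 |
|---|---|---|---|
| Day 1 | 1, 3, 8, 10 | 4 | 4/24 = 16.7% |
| Day 2 | 2, 4, 9, 11 (the last on the scan day, before the scan) | 4 | 16.7% |
| Day 5 | two between 5 and 11 | 2 | 2/24 = 8.3% |
| Day 8 | 8, 10 | 2 | 8.3% |

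Even spacing over 10 days gives 2 × 10/7 = 2.9 sessions, or 2.9/24 = 11.9%.

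**Effect on the measured difference, scan on the last permitted day.** Assume volume rises linearly with sessions, by *g* per session in the neck arm and *c* in the control arm, and that *k* sessions precede the scan in each arm.

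- True difference in gain: 24(*g* − *c*).
- Measured difference: (24 − *k*)(*g* − *c*).
- Proportion lost: *k*/24, which is 8.3% for *k* = 2 and 16.7% for *k* = 4.

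Linearity probably makes this an upper bound for true growth. The endpoint justification in Section 3 expects recruitment gains before hypertrophy, and Section 4.3 has volume and intensity rising over the programme, so early sessions should contribute less than their share.

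**Average over the window.** Assume scan dates uniform over the 21 calendar days and sessions on Days 2, 5, 9 and 12.

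- Sessions on days strictly before the scan: 1 for Days 3-5, 2 for Days 6-9, 3 for Days 10-11, otherwise 0. The sum is 3 + 8 + 6 = 17; 17/21 = 0.81 session; 0.81/24 = 3.4%.
- Counting a same-day session as before the scan: 1 for Days 2-4, 2 for Days 5-8, 3 for Days 9-11. The sum is 3 + 8 + 9 = 20; 20/21 = 0.95; 0.95/24 = 4.0%.
- The tightest pattern (Days 2, 4, 9, 11), same-day sessions counted: (2 × 1) + (5 × 2) + (2 × 3) + 4 = 22; 22/21 = 1.05; 1.05/24 = 4.4%.

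The average is therefore about 3% to 4%, and lower if training starts later.

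**Power.** Section 9.2 rests on log(net head acceleration), 30 per arm, and standardized effects of 0.6 to 1.0 multiplied by 1.25. A two-sided normal calculation at 0.05 gives 0.828 and 0.998, which matches the stated .83 and 1.0. MRI volume does not enter it.

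**The case against.** **Little depends on the scan.** The summary of changes says MRI is not used for the primary outcome, Section 2.3.1 says not everyone is scanned, and volume is also estimated from Day 1 measurements. Section 9.4 sets out no between-arm analysis of MRI volume change. All of this stands and keeps the point at exploratory level. Even so, Section 3 lists the effect of training on muscle volume as an exploratory objective, and MRI is the reference for the estimate.

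**The nominal date is Day 1, the MRI column precedes the exercise column, and ±10 days is a tolerance.** Late scans may well be uncommon. But column order is not a rule, and a Day 11 scan would not even count as a schedule deviation.

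**A reader might infer that only the neck arm's baseline can shift and that controls are unaffected.** The documents do not support this. Both arms train shoulders and back, and upper trapezius is one of the muscles measured. What differs by arm is the neck-specific loading.

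**A reader might also infer a large bias from post-exercise swelling.** Section 2.3.1 says "Subjects are anticipated to experience delayed-onset muscle soreness following resistance training". That concerns soreness after supervised sessions in general; it is not evidence of swelling in the neck. Swelling could equally be present at the final MRI, so its net direction is unknown. Any larger percentage would need an assumed swelling and an assumed 12-week gain, and the documents give neither.

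**Nor do the documents support a compulsory rest gap before every scan or laboratory visit.** Nothing here shows a problem at the laboratory visits, and such a rule would reach into exercise scheduling.

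**Conclusion.** The point holds as a minor defect that is cheap to remove. The window permits a baseline MRI after randomization and after roughly 2 to 4 of 24 sessions, no section prevents it, and this conflicts with the pre-exercise meaning of baseline in Section 9.4.4. The likely direction, for true growth only, is a smaller measured between-arm difference in MRI volume change.

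The size is at most 8% to 17% for someone scanned on the last permitted day and about 3% to 4% on average. These figures rest on an assumed first-session day and linear gain; the average also assumes uniform scan dates. The effect on the equation's validation is real in principle but cannot be sized from the documents. Conclusions about net head acceleration on the primary and secondary endpoints do not change.

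**What to change.** In Section 1.3, replace the baseline MRI window with: Day -10 up to, but before, the first exercise session. Sessions before the baseline scan then fall from a possible 4 of 24 to 0 of 24.

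For any scan already taken after session 1, record the number of sessions completed before it. Repeat the MRI volume-change analysis and the validation of the prediction equation without those scans, as a sensitivity analysis. The scans stay in the main data set, in line with the inclusion of partial data in Section 9.3.

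The cost is tighter scanner booking and possibly a few athletes without a pre-exercise baseline MRI. Sample size and power do not change. The new window still allows up to about 10 days between scan and Day 1 ultrasound, but no study exercise would fall between the scan and the Day 1 measurements.

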# 2 INTRODUCTION

## 2.1 STUDY RATIONALE

Neck strengthening exercise represents a simple and practical intervention to reduce the risk of sportrelated concussion (SRC) in the millions of student-athletes who play a high school sport in the US each year. Athletes whose necks are less able to attenuate forces acting on their heads during an impact will experience greater head acceleration and therefore be at higher risk for sustaining SRC. In fact, the only study to directly assess the neck's influence on concussion risk was a prospective epidemiological investigation demonstrating that for every one-pound increase in neck strength there was a 5% reduction in the odds of sustaining SRC. However, neck strengthening exercise remains under-utilized in the high school athlete population, and there is a gap in our understanding of how the neck influences an athlete's head acceleration under different impact conditions, as well as how these relationships may be modified by exercise. There is a critical need to define these relationships and to develop optimal neck strengthening exercise protocols for high school athletes to reduce their risk of SRC.

This work is expected to have a positive translational impact in the field because *evidence-based prescription of neck strengthening exercise represents a significant advancement over the existing status quo*, which ranges from an uninformed "shooting in the dark" approach to neck strengthening exercise prescription to no neck strengthening exercise at all. Based on our own pilot results and published epidemiological work, we estimate that neck strengthening exercise may have the *potential to prevent as many as 47,000 cases of SRC* in high school athletes annually. While this work will focus on high school soccer athletes, it will have translational potential to inform SRC prevention efforts in broader athlete populations, including youth and collegiate athletes, as well as athletes who participate in sports other than soccer.

# 2.2 BACKGROUND

#### **Clinical and Societal Significance**

Sport and recreation-related concussion (SRC) is a common injury estimated to affect as many as 3.8 million Americans each year, and is now recognized as a major public health concern in the U.S. In the short-term, SRC causes a constellation of physical, cognitive, affective, and sleep-related signs and symptoms limiting an athlete's ability to participate in academic, vocational, and recreational pursuits for a period of days to months. A history of SRC increases an athlete's risk for sustaining subsequent concussions in the short term, as well as for developing depression, dementia, and neurodegenerative diseases including chronic traumatic encephalopathy later in life. Given the myriad of negative short- and long-term consequences of SRC, developing injury prevention strategies is critically important.

The ~7.8 million student-athletes who participate in organized sports at the high school level each year represent the single largest population of athletes at risk for sustaining SRC. In fact, we recently reported in *JAMA* more than one out of every 5 U.S. high school students who participate in contact and semi-contact sports has sustained at least one prior concussion. Further, concussions represent approximately 13% of all athletic injuries in this population. High school-aged and younger athletes whose brains have yet to fully develop are also thought to have a greater physiological susceptibility to concussion than adults.

#### **Overall Scientific Premise**

This proposal is built upon the overall scientific premise that concussion occurs as a result of rapid head acceleration following external force application. An early explanation of the positive association between head acceleration and the risk of brain injury was provided by the Wayne State Tolerance Curve (WSTC), which demonstrated that injury risk increased with greater magnitudes and durations of linear head acceleration. Weaknesses of the WSTC include its failure to account for angular acceleration and its focus on more severe brain injury rather than SRC. More recently, our group and others have performed field-based concussion biomechanics research using a helmet-based head impact sensor [Head Impact Telemetry (HIT) System] further supporting the relationship between head acceleration and the associated risk of SRC.5, 7, 18, 23, 68 We have recently published two reviews summarizing that body of work, which now includes over 40 peer-reviewed scientific publications. The HIT System provides the best *in vivo* biomechanical head impact data available today. but is limited by measurement error associated with imperfect coupling of the in-helmet sensors to the head. Furthermore, most studies using the HIT System have given relatively little consideration to impact durations. Field-based biomechanics research provides an unparalleled ability to collect head acceleration data in vivo, but has failed to demonstrate a simple linear or angular acceleration threshold able to reliably discriminate between concussive and non-concussive head impacts. Nonetheless, it is clear the risk of concussion associated with a given impact increases with increasing linear and angular head acceleration magnitudes and durations.66

Head acceleration causes concussion by inducing brain tissue deformation that leads to microstructural and physiological injury. Since greater head acceleration magnitudes and durations both increase brain tissue deformation, *this provides a mechanistic explanation for the observed relationship between head acceleration and concussion*.

**Scientific Premise for AIM 1:** *AIM 1 is based on the scientific premise that attributes of an athlete's cervical muscles (i.e., neck strength, cervical muscle volume and neuromuscular recruitment patterns) influence their risk of SRC for a given impact by modifying the resultant acceleration of their head. Therefore, neck strengthening exercise has the potential to mitigate head acceleration during sport-associated impacts to reduce an athlete's SRC risk.* The strongest evidence that the neck can influence an athlete's risk of SRC comes from a large epidemiological study involving 6,704 high school male and female soccer, basketball, and lacrosse athletes. In that study there was a 5% decrease in

odds of SRC for every one-pound increase in neck strength. However, that study did not address the mechanism relating neck strength to concussion risk so it cannot directly inform the development of neck strengthening exercise programs. In contrast with that epidemiological evidence, two *in vivo* studies using the HIT System to measure head acceleration magnitudes as a proxy measure for concussion risk failed to support the hypothesis that having a larger, stronger neck is associated with lower head accelerations in American football and ice hockey athletes in the field. While these field-based studies share strong ecological validity, a major weakness of both studies was their lack of experimental control. Because impact conditions were not monitored, factors known to influence head acceleration, such as impact anticipation and bracing, may have confounded any underlying association between cervical muscle attributes and head acceleration.

Taking advantage of the greater experimental control achieved in a laboratory environment, we have previously reported on the influence of neck strength and circumference on head accelerations in response to standardized test loads. In 46 male and female contact sport athletes exposed to standardized loads in each plane of motion, we found greater neck strength and circumference were both significantly associated (r= .42 to r= .76) with lower head acceleration, quantified in that study as the changes in linear and angular velocity ( $\Delta V$  in m/s and  $\Delta \omega$  in °/s) to account for both acceleration magnitude and duration given their mathematical equivalence to the areas under the linear and angular acceleration curves. Other groups have used similar laboratory-based methodologies to administer sagittal-plane standardized test loads to subjects' heads in pursuit of complementary study aims with similar results. Such experimental designs allow researchers to safely and precisely apply standardized test loads directly to the head, while measuring resultant linear and angular head accelerations with a high degree of accuracy. However, with this standardization, precision, and control comes the loss of ecological validity as such testing paradigms do not closely mimic the circumstances athletes experience during live sport participation. One approach to improving ecological validity while maintaining a high degree of experimental control is to study simulated sport-specific events in a lab environment. Several studies have adopted this approach to either directly or indirectly assess relationships between various cervical attributes and head acceleration during lab-based soccer heading tasks, typically reporting significant associations between greater neck strength and/or circumference and lower head acceleration. However, no study has investigated the effect of a neck strengthening intervention on head acceleration using a soccer heading model.

The strongest direct support for the premise that neck strengthening exercise will decrease head acceleration during sport-associated impacts comes from our own group's pilot data collected in 17 male and female youth and high school athletes. In our pilot study, 13 participants assigned to a supervised 8-week manual resistance neck strengthening exercise program had greater increases in neck strength than 4 participants assigned to a control resistance exercise program not specifically targeting the neck. Athletes in both groups experienced decreases in head acceleration, again quantified as  $\Delta V$  and  $\Delta \omega$ . Multiple other researchers have also demonstrated increases in neck strength and circumference with resistance training, but only one other published study has reported the effect of neck strengthening exercise program or a control program not including cervical resistance exercises. The neck strengthening exercise group demonstrated increases in neck strength and circumference, but without a corresponding decrease in peak angular head acceleration during standardized loading in flexion and extension.

Unfortunately, there are limitations associated with both of those interventional studies. A limitation of our own pilot neck strengthening study was its small, unbalanced sample size, which limits statistical power and the generalizability of our results. Furthermore, because we did not measure the resistance applied by the strength coach during the manual resistance exercises, we were unable to assess for evidence of dose-response relationships. The Mansell et al. study was likely limited by a ceiling effect due to its inclusion of only highly-trained Division I collegiate athletes. A potential ceiling effect is supported by our own data demonstrating non-linearity in the relationship between neck strength

and head acceleration. Furthermore those results may not generalize to non-collegiate populations. In addition, that exercise intervention addressed only the sagittal plane, and only sagittal-plane angular head acceleration magnitude was considered as a kinematic outcome. Finally, neither study's laboratory-based standardized test loads were representative of head impact events encountered by athletes during sport participation in the field. *There remains a knowledge gap in how neck strengthening exercise influences an athlete's head acceleration during sport-associated impacts.* 

AIM 1 will directly address this knowledge gap by determining the effect of manual resistance neck strengthening exercise on net head acceleration during direct force application to the head, force application to the body with inertial force transmission to the head via a simulated checking/blocking task, and voluntary soccer heading. In designing AIM 1, we have addressed each of the limitations in the previous studies described above.

Scientific Premise for AIM 2: AIM 2 is based on the scientific premise that anticipatory precontraction of the cervical muscles to brace for an impact influences head acceleration. Furthermore, cervical muscle attributes (i.e., neck strength and cervical muscle volume) influence head acceleration differently with vs. without cervical muscle pre-contraction. This premise is supported by our own work demonstrating that head acceleration, again reported as  $\Delta V$  and  $\Delta \omega$ , decreased by 12.3% and 9.7%. respectively, during anticipatory cervical muscle pre-contraction as compared to relaxed, upright sitting. Recent finite element modeling work, as well as numerous other studies in the concussion and whiplash literature, have also reported decreased head acceleration in response to various forms of loading during trials with vs. without anticipation and/or cervical muscle pre-contraction. However, the design of those studies limits the insight they can provide into which cervical muscle attribute is most responsible for controlling head acceleration with vs. without anticipatory pre-contraction. While not the primary objective, our previous work demonstrated greater neck strength and circumference were each significantly associated with lower  $\Delta V$  and  $\Delta \omega$  across all directions of head motion under both anticipation conditions (r= .42 to r= .60 for neck strength; r= .60 to r= .76 for neck circumference). In that study, more of the variability in head acceleration was explained by neck strength for 6 of the 7 models under the anticipated condition, but by neck circumference for 6 of the 7 models without anticipation. That finding suggests neck strength and cervical muscle volume may influence head acceleration differently depending on cervical muscle pre-contraction status. We are unaware of other reports to directly quantify the relationships between individual cervical muscle attributes and head acceleration with vs. without anticipatory cervical muscle pre-contraction.

The premise that neck strength and cervical muscle volume may exert differential influences on head acceleration during anticipated vs. unanticipated impacts is further supported when considering each potential cervical contributor to head acceleration. Previous work concluded that since the mechanical properties of the neck's non-contractile tissues (e.g., bone, ligament) are not affected by muscle activation, and because peak head acceleration is reached before either a reflexive or voluntary muscular response has had time to occur, head acceleration is primarily influenced by the mechanical properties of the cervical muscles. Passive muscle stiffness is strongly influenced by the amount of muscle tissue being acted upon. In contrast, the stiffness of actively contracting muscle increases proportionally with muscle activation and torque. Therefore for any volume of cervical muscle, greater neck strength (i.e., torque generation) associated with improved neuromuscular recruitment is expected to confer greater muscle stiffness during maximal anticipatory cervical muscle pre-contraction to brace for the impact. While muscle strength and volume co-vary, these characteristics are known to change independently from one another with aging, disuse, and of greater direct applicability to this proposal, following resistance training. There remains a knowledge gap in how individual cervical muscle attributes affect head acceleration during sport-associated impacts with vs. without anticipatory cervical muscle pre-contraction to brace for the impact.

AIM 2 will directly address this knowledge gap by comparing the relative weights of neck strength and cervical muscle volume in predicting net head acceleration during anticipated and unanticipated impacts to the head and body.

